5 PROCEDURES

5.1 Study procedures. Using lay language, provide a complete description of the study procedures, including the sequence, intervention or manipulation (if any), time required, and setting/location. If it is available and you think it would be helpful to the IRB: Upload a study flow sheet or table to the **Supporting Documents** SmartForm in **Zipline**.

For studies comparing standards of care: It is important to accurately identify the research procedures. See UW IRB [POLICY: Risks of Harm from Standard Care](#) and the draft guidance from the federal Office of Human Research Protections, ["Guidance on Disclosing Reasonably Foreseeable Risks in Research Evaluating Standards of Care"](#); October 20, 2014.

Preliminary Performance Review

The initial step will include a performance review of 50 FP clinics, purposively sampled to include a range of large and small, public and private, urban, peri-urban, and rural facilities. We will use routinely reported data in the FP Registers to measure the proportion of new clients counselled and tested for HIV. These data will be used to assign a performance score to each clinic, as shown in [Figure 6](#). This will also help to confirm that different clinics are using the same registers. If multiple registers are identified, then we will keep records of the different versions that exist and compare between registers when able.

Figure 6: Definitions & Calculation of Performance Score Using Data from FP Register

HIV Counseling	Numerator: Number of new FP clients counselled about HIV testing in the past 3 months Denominator: Total number of new FP clients in the past 3 months	Score 1
HIV Testing	Numerator: Number of eligible (not known HIV+) new FP clients tested for HIV in the past 3 months Denominator: Total number of eligible (not known HIV+) new FP clients in the past 3 months	Score 2
Overall Performance	Score 1 X Score 2: The product of the two proportions will fall on a 0-100 distribution	Score 3

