While HIV testing in new clients is our primary outcome, we feel that a performance score incorporating both counseling and testing may provide a better baseline measure of performance. Nonetheless, we will also consider the individual *HIV Counseling* and *HIV Testing* scores if they do not tend to track together, and will adapt our randomization accordingly. If too few clinics perform any HIV counseling or testing, we will choose alternative measures of performance in the FP Register, such as recording of client number, client type (new/revisit), age, telephone number, and village/landmark. The rationale for conducting this initial step in 50 clinics, rather than just the 24 needed for completion of the RCT, is to provide a larger sample to enter the restricted randomization process. Preliminary examination of these data will allow us to fine-tune our choice of variables on which to balance the study arms and to optimize the planned length of outcome evaluation periods to capture sufficient endpoints. If any clinics seem inappropriate for participation (e.g. planned closure or unmatchable outliers), they may be removed prior to the randomization.

Aim 1:

In the 12 intervention facilities, the study team will first work with FP clinic staff and managers to identify one or more sets of best practices, which will help to guide the subsequent iterative process improvement steps. A combination of quantitative, qualitative, observation, and flow-mapping data will be used for this purpose

Quantitative data: We will collect data on health system factors that could influence facility performance. We will develop a standardized reporting form, refining assessment items according to current implementation experience, but expect to cover domains including commodities, facility characteristics, human resources, information systems, management, and structure of linkage to HIV

care.

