Step 3: Define and implement workflow adaptations to eliminate modifiable bottlenecks. This step will involve development of a written implementation plan addressing the questions, “Who will be responsible for implementing the intervention?”, “What activities will be initiated?” and “What materials/inputs are needed for the intervention?” (56). Small costs for materials/inputs can be covered from the grant budget and tracked for the costing and budget impact analysis. Interventions will be conceived by clinic staff and management with support from study staff using a combination of best practices from the intervention guide and context specific adaptations based on strengths and challenges at individual facilities.

Step 4: Monitor change in performance. The goal of this step is for staff and managers to effectively use routinely collected data to understand the impact of workflow adaptations on the movement of patients through the system. Data from one to two months will be evaluated using the Excel-based tool introduced in *Step 1*. A graphic time-series display of key outcome data will be created to visually depict improvements.

Step 5: Repeat the analysis and improvement cycle (steps 1-4). This step reflects the concept that workflow quality improvement is a continuous and iterative process, with each new cycle of innovation, testing, and learning building on prior cycles (53). Multiple cycles will be completed over a period of 12 months.

At control clinics, we will collect the same information from the FP register as the intervention arm (contraceptive method, age, client type, HIV counselling, HIV tested and HIV status), periodically, but not more often than every three months. We do not want to collect these too frequently, as this observation alone might have some intervention impact on the control clinics (Hawthorne Effect).

[figure not shown]

Figure 7. Example of Microsoft Excel-based analysis tool for identifying facility-level bottlenecks in the care cascade

Randomization:

Randomization will be performed by a statistician from our CFAR biometrics core, who does not have any other role in this study. We will use a restricted randomization that considers all possible combinations where the clusters are balanced on new client volume and performance score, then randomly selects one of these combinations as the randomization. This allows analysis of the data as if they were unmatched.

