Disclaimer: Due to restrictions on human subject research as a result of the COVID-19 pandemic, most activities for Aim 2, which began in February 2020, were on hold between March and August 2020. Activities resumed in September 2020, but were interrupted again by a strike, in response to unpaid wages and lack of PPE in the context of the COVID-19 pandemic. This has led to a number of our FP clinics being unable to participate in the trial for portions of the original 12-month period described in the Aims and Study Procedures. As a result, Aim 2 data collection will be extended an additional 6 months, for a total of 18 months of data collection for Aim 2.

5.2 Data variables. Describe the specific data you will obtain (including a description of the most sensitive items). If you would prefer, you may upload a list of the data variables to the **Supporting Documents** SmartForm instead of describing the variables below.

The primary outcome will be the proportion of eligible (not known HIV+) new FP clients who are tested for HIV during the evaluation periods at the end of 12 months of SAIA training and following an additional year in which intervention clinics are encouraged to continue to implement the SAIA intervention with minimal support from the study team. The secondary outcome will be the proportion of new FP clients who are counseled about HIV testing. When data are not filled, we will assume the counseling or testing has not been done. While we recognize that there are few variables available in implementation research datasets (e.g. clinic size, public/private, rural/urban), these variables will be collected for comparison of the randomization arms to assess balance across intervention groups.

Our primary analysis will follow the intent-to-treat principle. The proportion of eligible new FP clients tested for HIV and the proportion of new FP clients counselled about HIV testing will be compared in intervention versus control facilities using generalized estimating equations with a binary link, clustered by clinic. Because there will be more than a year between the first and second assessments, we anticipate that these will take place as separate analyses, as they are completed.

5.3 Data sources. For all types of data that you will access or collect for this research: Identify whether you are obtaining the data from the subjects (or subjects' specimens) or whether you are obtaining the data from some other source (and identify the source).

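### The primary GEE on 24 clinics names no small-sample correction, reference distribution, working correlation or covariates, so its true level is not controlled and could fall on either side of 5%

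*Combined protocol and SAP*

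**What the plan says.** The primary analysis is one sentence in Section 5.2. Under intent-to-treat, testing and counselling proportions are compared between arms "using generalized estimating equations with a binary link, clustered by clinic". Aim 1 (Section 1.5) sets 12 clinics per arm. HYP 2 in the same section predicts significantly higher rates, so a significance test is intended. No section gives a variance correction, reference distribution, working correlation, covariate, alpha, ICC, target effect or power. The phrase used for the link does not identify a link function or an effect measure.

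Section 5.1 (Randomization) chooses at random among allocations in which "the clusters are balanced on new client volume and performance score", and adds: "This allows analysis of the data as if they were unmatched". Figure 6 builds the score from baseline counselling and baseline testing: "The product of the two proportions will fall on a 0-100 distribution". Two provisions leave the balancing factors open. If too few clinics counsel or test, "we will choose alternative measures of performance in the FP Register", and the preliminary data may be used to "fine-tune our choice of variables on which to balance the study arms". Section 5.2 gives clinic variables such as size and public/private status one use: "these variables will be collected for comparison of the randomization arms to assess balance across intervention groups".

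**The concern.** Two omissions meet here, and they act in opposite directions.

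- **Few clusters.** With 24 clinics, an uncorrected sandwich variance is too small on average, and a normal reference is too narrow. Unequal clinic sizes make this worse under independence working correlation, and Section 2.2 seeks a wide range of sizes. This pushes the true level above nominal.
- **Restricted allocation, no adjustment.** If the score predicts the endpoint, balancing on it reduces the real variability of the arm difference. An unadjusted standard error does not reflect that reduction. This pushes the true level below nominal and wastes precision that the design has already bought.

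The plan fixes neither, so a reader cannot tell whether a reported p-value comes from a liberal or a conservative test. The same sentence governs the testing outcome, the counselling outcome and the separate Aim 2 analysis.

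**Working it through.** The plan has no power or error figure to reproduce.

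**1. Small-sample effect alone.** Refer a t(22) statistic (24 clinics - 2 parameters) to 1.96:
- 2 x P(t22 > 1.96) = 0.063.
- Add the (m - 1)/m bias of the sandwich variance at m = 12 per arm: 2 x P(t22 > 1.96 x sqrt(11/12)) = 0.074.

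**2. Inputs for the simulation.**
- From the plan: 12 v 12 clinics and 38,418 new clients at 194 clinics in 2014. 38,418/194/12 = 16.5 per clinic per month, or 49.5 over three months, so a mean of 50 is used. Section 2.1 states 21 per month, which would give 63.
- Assumed, because the plan gives none: two-sided 5%, ICC 0.10, size CV 0.8, 20% tested, a three-month window, the best 10% of allocations kept, and the score-outcome correlation r.

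**3. Model and tests.** Clinic counts are beta-binomial. The score is tied to the clinic's endpoint proportion by a normal copula. Allocations are ranked on standardized differences in score and log volume. For the identity link the clinic weight is w = n/(1 + (n - 1)rho), with rho = 0 (independence) or a moment estimate (exchangeable). With M = (X'WX)^-1, the sandwich is M[sum of w²e²xx']M. Kauermann-Carroll (KC) divides e² by 1 - h, where h = w x'Mx. The adjusted model has intercept, arm, score and volume, so the reference is t on 24 - 4 = 20.

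**4. Type I error (%), 20,000 replicates, Monte Carlo SE about 0.15.**

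| Test | r = 0 | 0.3 | 0.5 | 0.7 | 0.85 |
|---|---|---|---|---|---|
| Unadjusted, uncorrected z, exchangeable | 8.1 | 6.9 | 5.2 | 3.0 | 1.2 |
| Unadjusted, uncorrected z, independence | 10.2 | 9.5 | 7.7 | 5.6 | 3.5 |
| Correction only, KC t(22), exchangeable | 5.7 | 4.7 | 3.3 | 1.8 | 0.7 |
| Both, KC t(20), exchangeable, identity link | 5.6 | 5.4 | 5.5 | 5.5 | 5.4 |
| Permutation over acceptable allocations | 5.3 | 5.0 | 5.0 | 4.8 | 4.7 |

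Adjustment without correction ran about 8-10% under exchangeable across separate implementations.

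**5. Tightness (keeping 10 / 25 / 50 / 100% of allocations), uncorrected and unadjusted.**
- Exchangeable: 5.2 / 6.0 / 6.0 / 8.0% at r = 0.5, and 1.2 / 1.8 / 2.6 / 8.3% at r = 0.85.
- Independence: 7.7 / 8.8 / 8.6 / 10.4% at r = 0.5, and 3.5 / 4.4 / 5.4 / 10.4% at r = 0.85.

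The direction therefore depends on working correlation, prognostic strength and tightness together. Section 5.1 reviews 50 clinics "to provide a larger sample to enter the restricted randomization process". Letting the draw also pick 24 of 50 gives 8.0 / 7.1 / 5.7 / 2.9 / 1.3% for the exchangeable test, much the same.

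**6. Nominal power (%), assumed 20% v 35%, ICC 0.10, exchangeable; 8,000 replicates, SE about 0.5.**

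| Test | r = 0 | 0.5 | 0.7 |
|---|---|---|---|
| Uncorrected, unadjusted | 69 | 70 | 71 |
| Correction only | 62 | 62 | 63 |
| Both | 61 | 70 | 81 |
| Permutation | 59 | 66 | 76 |

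Both parts against the uncorrected test: 61 - 69 = -8, 70 - 70 = 0, 81 - 71 = +10. At r = 0 the uncorrected test's own error is about 8%.

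The gain of both parts over correction only at r = 0.5 varies with ICC: about 4 points at 0.05 (84% to 88%), 8 at 0.10 (62% to 70%) and 10 at 0.20 (38% to 47-48%).

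**The case against.** - **The plan never says that the test is uncorrected.** True. A reader might infer that type I error is inflated, but the documents do not support that. They name neither the variance estimator nor the software, and even the default test can fall well below 5%.
- **Section 5.1 appears to settle adjustment.** A reader might infer that "This allows analysis of the data as if they were unmatched" rules covariates out, or that leaving the factors out inflates error. Neither follows. The sentence supports not using a matched analysis and does not address covariates. Leaving out prognostic balancing factors makes the test conservative.
- **A reader might claim that the plan loses 8 points of power (62% v 70%).** That compares correction alone with both parts, and neither is the assumed default. Against the default, the change at r = 0.5 is about nil in both error and power for exchangeable.
- **The score may not be prognostic.** This stands. It contains baseline testing, but other register items may replace it, and no correlation is given. If it is not prognostic, adjustment itself costs about 1 point of power (62% to 61%).
- **All inputs are assumed.** This stands. The sizes are illustrative. That the level moves with choices the plan leaves open does not rest on any one input.
- **Aim 2 may have lost clinics.** The Section 5.1 disclaimer reports lost clinic time and extends collection by six months. It does not say that clinics dropped out, so none is assumed lost.

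**Conclusion.** The point holds as a specification gap that should be fixed; it is not a demonstrated error inflation. If the sentence in Section 5.2 is run as a default uncorrected, unadjusted GEE, the true level of a nominal 5% test is about 8% (exchangeable) or 10% (independence) when the score is not prognostic, about 5% or 8% at correlation 0.5, and about 1% or 3.5% at 0.85. These figures rest on ICC 0.10, mean 50 clients, CV 0.8, 20% tested, the best 10% of allocations and two-sided 5%, all assumed except the mean size, which uses the plan's client counts and an assumed three-month window. The net direction is unknown, and is about nil in the central exchangeable case. The benefit of the fix is a level near 5% whatever the score's strength, and more power only if the score is clearly prognostic. Confidence is moderate, because the plan supplies none of the key inputs.

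**What to change.** Replace the analysis sentence in Section 5.2 with wording such as:

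> Arms are compared by GEE with [named link, effect measure and working correlation], adjusted for the clinic-level factors actually used in the restricted randomization (planned: performance score and new client volume), with a small-sample-corrected sandwich variance (for example Kauermann-Carroll) and a t reference on clinics minus clinic-level parameters (24 - 4 = 20), at two-sided alpha [value]. The same rule applies to the counselling outcome and to Aim 2. Any choice made after Aim 1 data were seen is labelled as such.

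On the GEE route, use correction and adjustment together: adjustment alone is liberal, and correction alone is conservative when the score is prognostic. A permutation test over the acceptable allocations can stand alone, if that set was saved or can be regenerated from the balance criteria.

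Costs and limits:
- No new data are needed, because score and volume were collected for randomization. The change is wording and a software option.
- About 8 points of nominal power are lost if the score is not prognostic. About 7 of these come from the correction (69% to 62%).
- The link is the team's choice. A logistic model performed similarly at 20-50% tested, but its adjusted, corrected test ran 7.6-7.9% when only 5% are tested.
- Exchangeable working correlation weights clinics more evenly than clients. At ICC 0.10, clinics of 10 and 100 clients get weights 10/1.9 = 5.3 and 100/10.9 = 9.2. Section 5.2 defines the outcome as a proportion of clients, so state the target if the effect may vary with clinic size.
- Aim 2 began in February 2020, so randomization is past. If Aim 1 has been analysed, pre-specification may be possible only for Aim 2.

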6.1 Involvement of minors. Does your research include minors (children)?

Minor or child means someone who has not yet attained the legal age for consent for the research procedures, as described in the applicable laws of the jurisdiction in which the research will be conducted. This may or may not be the same as the definition used by funding agencies such as the National Institutes of Health.

- In Washington State the generic age of consent is 18, meaning that anyone under the age of 18 is considered a child.
- There are some procedures for which the age of consent is much lower in Washington State. See the [WORKSHEET: Children](#) for details.
- The generic age of consent may be different in other states, and in other countries.

No → If no, go to [Section 8](#).

Yes → If yes, provide the age range of the minor subjects for this study and the legal age for consent in your population(s). If there is more than one answer, explain.

Don't know → This means it is not possible to know the age of your subjects. For example, this may be true for some research involving social media, the Internet, or a dataset that you obtain from another researcher or from a government agency. Go to [Section 8](#).

6.2 Parental permission. Parental permission means actively obtaining the permission of the parents. This is not the same as "passive" or "opt out" permission where it is assumed that parents are allowing their children to participate because they have been provided with information about the research and have not objected or returned a form indicating they don't want their children to participate.

a. Will you obtain parental permission for:

All of your research procedures → Go to [question 6.2b.](#)

None of your research procedures → Use the table below to provide your justification, and skip question 6.2b.

Some of your research procedures → Use the table below to identify the procedures for which you will not obtain written parental permission.

Be sure to consider all research procedures and plans, including screening, future contact, and sharing/banking of data and specimens for future work.

Children Group ¹	Describe the procedures or data/specimen collection (if any) for which there will be NO parental permission	Reason why you will not obtain parental permission	Will you inform them about the research? ²	
			YES	NO
				
				
				
				
				
				

Table footnotes

1. If your answer is the same for all children groups or all procedures, you can collapse your answer across the groups and/or procedures.
2. Will you inform them about the research beforehand even though you are not obtaining active permission?

b. Indicate by checking the appropriate box(es) your plan for obtaining parental permission

Both parents, unless one parent is deceased, unknown, incompetent, or not reasonably available; or when only one parent has legal responsibility for the care and custody of the child

One parent, even if the other parent is alive, known, competent, reasonably available, and shares legal responsibility for the care and custody of the child.

This is all that is required for minimal risk research.

If you checked both boxes, explain:

6.3 Children who are wards. Will any of the children be wards of the State or any other agency, institution, or entity?

No

**Yes**

→ If yes, an advocate may need to be appointed for each child who is a ward. The advocate must be in addition to any other individual acting on behalf of the child as guardian or in loco parentis. The same individual can serve as advocate for all children who are wards.

Describe who will be the advocate(s). Your answer must address the following points:

- Background and experience
- Willingness to act in the best interests of the child for the duration of the research
- Independence of the research, research team, and any guardian organization

7 ASSENT OF CHILDREN (MINORS)

Go to [Section 8](#) if your research does not involve children (minors).

7.1 Assent of children (minors). Though children do not have the legal capacity to “consent” to participate in research, they should be involved in the process if they are able to “assent” by having a study explained to them and/or by reading a simple form about the study, and then giving their verbal choice about whether they want to participate. They may also provide a written assent if they are older. See [WORKSHEET: Children](#) for circumstances in which a child’s assent may be unnecessary or inappropriate.

a. Will you obtain assent for:

 All of your research procedures and child groups	→ Go to question 7.2.
<hr/>  None of your research procedures and child groups	→ Use the table below to provide your justification, then skip to question 7.5.
<hr/>  Some of your research procedures and child groups	→ Use the table below to identify the procedures for which you will not obtain assent.

Be sure to consider all research procedures and plans, including screening, future contact, and sharing/banking of data and specimens for future work.

Children Group ¹	Describe the procedures or data/specimen collection (if any) for which assent will NOT be obtained	Reason why you will not obtain assent

Table footnotes

1. If your answer is the same for all children groups or all procedures, you can collapse your answer across the groups and/or procedures.

7.2 Assent process. Describe how you will obtain assent, for each child group. If your research involves children of different ages, answer separately for each group. If the children are non-English speakers, include a description of how you will ensure that they comprehend the information you provide.

7.3 Dissent or resistance. Describe how you will identify a child's objection or resistance to participation (including non-verbal indications) during the research, and what you will do in response.

7.4 Documentation of assent. Which of the following statements describes whether you will obtain documentation of assent?

None of your research procedures and child groups

→ Use the table below to provide your justification, then go to question 7.4.a.

All of your research procedures and child groups

→ Go to [question 7.4.a](#), do not complete the table

Some of your research procedures and/or child groups

→ Complete the table below and then go to question 7.4.a

Children Group ¹	Describe the procedures or data/specimen collection (if any) for which assent will NOT be documented	Reason why you will not document assent

Table footnotes

1. If your answer is the same for all children groups or all procedures, you can collapse your answer across the groups and/or procedures.

a. **Describe how you will document assent.** If the children are functionally illiterate or are not fluent in English, include a description of what you will do.

b. **Upload all assent materials** (talking points, videos, forms, etc.) to the **Consent Form and Recruitment**

Materials SmartForm of **Zipline**. Assent materials are not required to provide all of the standard elements of adult consent; the information should be appropriate to the age, population, and research procedures. The documents should be in Word, if possible.

7.5 Children who reach the legal age of consent during participation in longitudinal research.

Children who were enrolled at a young age and continue for many years: It is best practice to re-obtain assent (or to obtain it for the first time, if you did not at the beginning of their participation).

Children who reach the legal age of consent: You must obtain informed consent from the now-adult subject for (1) any ongoing interactions or interventions with the subjects, or (2) the continued analysis of specimens or data for which the subject's identify is readily identifiable to the researcher, unless the IRB waives this requirement.

a. Describe your plans (if any) to re-obtain assent from children.

b. Describe your plans (if any) to obtain consent for children who reach the legal age of consent.

- If you plan to obtain consent, describe what you will do about now-adult subjects whom you are unable to contact.
- If you do not plan to obtain consent or think that you will be unable to do so, explain why.

7.6 Other regulatory requirements. (This is for your information only; no answer or response is required.)

Researchers are responsible for determining whether their research conducted in schools, with student records, or over the Internet comply with permission, consent, and inspection requirements of the following federal regulations:

- PPRA – Protection of Pupil Rights Amendment
- FERPA – Family Education Rights and Privacy Act
- COPPA – Children's Online Privacy Protection Act

